Relevant Experience Examining Menstrual Cycle/Ovarian Hormone Effects on Craving/Smoking Behavior. Our initial efforts to understand the role of sex hormones in smoking focused on menstrual cycle phase effects on smoking-related craving and cue reactivity (Gray, et al., 2010). In this study, female smokers ($n=37$) received a smoking cue reactivity assessment during each of four biologically verified phases of the menstrual cycle: early- and mid-follicular and mid- and late-luteal. Stimuli presented during the cue reactivity assessments were in vivo smoking cues, which consisted of manual handling of the participant's preferred brand of cigarettes, and scripted stressful/negative affect cues, which consisted of an personalized imagery script of a stressful event in the participants recent past. Control cues for the smoking and stress/negative affect cues consisted of the handling of pencils & eraser and a relaxing imagery script, respectively. Results indicated significant variation across the cycle, with craving to smoking cues elevated in the follicular phases, relative to the luteal phases ($p = .02$). Heart rate reactivity to stressful/negative affect cues ($p = .01$) and skin conductance reactivity to smoking cues ($p = .05$) varied across cycle phases as well, with maximum reactivity occurring during the mid-follicular phase. These findings, taken together, demonstrated elevated reactivity during at least part of the follicular phase, but it remained unclear what underlying ovarian hormone fluctuations might be contributory. While other studies (Sofuoglu, Babb, & Hatsukami, 2001; Sofuoglu, Mouratidis, & Mooney, 2011) have suggested that progesterone, which is present in higher levels during the luteal phase relative to the follicular phase, may have a protective effect against craving, it remained unclear whether progesterone effects may be static versus dynamic (i.e., related to absolute level at a given time point versus change in level over time), or whether estradiol might also contribute.

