Individuals interested in the study will receive a brief telephone screening to determine if they may be eligible to participate. They will then be scheduled for an initial assessment session, consisting of an informed consent procedure, followed by completion of medical history, physical exam, self-report questionnaires, and semi-structured interviews to determine study eligibility. If volunteers complete the informed consent process and are eligible for participation, they will be enrolled in the study. A comprehensive battery of instruments will be administered to characterize participants' smoking, stressor exposure history (past and current), and general psychiatric functioning (see Instruments/Measures, Section C3g.). The research team will use several methods of contact to keep in touch with participants. We will ask them to provide us with phone numbers, e-mail

addresses, current home and work addresses, and contact information of family and friends who may know how best to reach them. We will also have a Facebook account that we may use to contact participants. The research team will only use private messages to contact participants through Facebook

We considered incorporating luteinizing hormone home testing kits to randomize female participants to start study procedures at the outset of the follicular or luteal menstrual cycle phase, but opted not to for multiple reasons. First, we noted in our initial SCOR study that the associated lag in initiation of study procedures for some women was associated with relatively high dropout rates. Additionally, the proposed study will enroll both men and women and we wanted to avoid using any menstrual phasing procedures that would result in substantially different treatment of male and female participants (i.e., long delays before the occurrence of study procedures for some females but no delays for other females and all males). Second, we noted in our subsequent SCOR study that enrolling a similarly sized sample of women resulted in an even distribution of enrollees across the menstrual cycle (while also resulting in improved participant retention rates). We also felt it important to progress from a “follicular versus luteal” phase approach to a continuous measurement approach involving the direct assessment of hormone levels. Therefore, we elected to use a participant enrollment approach that will allow women to enroll at any time/stage of the menstrual cycle.

C3d. Training Procedures.

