This study is powered to test the hypothesis that non-cigarette-deprived females will be more reactive to smoking cues than males, as measured in the natural environment of smokers via CREMA technology. However, the sample size obtained for this is adequate to test all the four hypotheses with at least 80% power. The justifications for the power calculations are as follows. A recent study (Heishman, et al., 2010) found that non-cigarette-deprived females responded to smoking cues with 10% greater craving than males (i.e., 10-unit difference on a 100-mm VAS), with this difference corresponding to an effect size of $d = 0.7$. Since the proposed design intends to assess gender differences in a non-laboratory setting, we have reduced the expected effect size by 30% to 0.50. Based on the four-item subscale of the QSU (cf., Warthen & [name], 2009b) to be used in the proposed study, a comparable detectable gender difference would be 0.45 ($sd=0.9$). Accounting for the multiple correlated measures within each participant (i.e., reactivity will be measured multiple times daily for 14 days using CREMA) through a between-observation correlation (autocorrelation) of 0.70, a sample of 96 females and 48 males is necessary to achieve 90% power (with a two sided type I error rate of 0.05) to detect the minimum relevant effect size of $d=0.50$. It is estimated that up to 20% of the participants may be lost before completion of the study.

Assuming 144 participants complete all study procedures (accounting for 20% dropout), we will also have 80% power with a type I error of 0.05 to detect a minimum effect size of $d=0.50$ between females and males in stress and craving response to the TSST and similarly between the oxytocin and placebo groups.

C3j. Data Management & Statistical Analysis.

Data Management

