menses. Linear models may thus be inappropriate. Traditional analyses group the hormone curves based on the estimated phases of women's menstrual cycle (follicular and luteal) for the analyses. In addition to performing the data analyses using the same method, analysis will be extended to incorporate the non-linear patterns of an individual's hormone profile. This method will be based on a non-linear regression model that has two to three segments, each one of which may be either quadratic or linear (Marrie, Dawson, & Garland, 2009). The 'joint-points' at which the segments meet, which are referred to as knots, will also be treated as unknown and determined through the modeling process. After identifying the segments, regression models assessing hormone measures against the outcome (e.g., cue-elicited craving) in each segment will be assessed and the results interpreted accordingly.

Aim 2: Hypotheses 1 and 2 - To test for gender and medication (oxytocin versus placebo) effects on reactivity profiles to the TSST during the laboratory session, a linear mixed effects model in which the dependent variables of interest are craving, stress and neuroendocrine (cortisol) response, and the primary independent fixed effects are gender, treatment group, and a random subject effect will be utilized. To account for the repeated measures, a covariance pattern for the error structure (such as an AR(1)) will be considered. The primary goal of this analysis will be to determine if the response to TSST is significantly different between females and males and/or significantly different between those who received oxytocin versus placebo (main effects of gender and medication). Additionally, as a secondary analysis, the interaction between gender and medication condition will be explored.

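### Aim 1 Hypothesis 2 has two analyses and no named deciding test, and the added segment analysis gives several hormone slopes that are never combined into a test of the estradiol/progesterone ratio

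*Combined protocol and SAP*

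**What the plan says.** The Specific Aims state Hypothesis 2 of Aim 1 as a single directional relation in women: the higher the estrogen/progesterone ratio, the stronger the craving response to stressful and smoking cues.

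Section C3j gives the analysis. It observes that hormone curves are not linear over time and infers that linear models may not be suitable. It keeps the traditional follicular/luteal grouping and adds "a non-linear regression model that has two to three segments, each one of which may be either quadratic or linear", with the knots estimated from the data. The last step is: "regression models assessing hormone measures against the outcome (e.g., cue-elicited craving) in each segment will be assessed and the results interpreted accordingly".

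Other relevant places:
- C3j and section 1.1 (Human Subjects Involvement): observation lasts 14 days, and eligible cycles run 25 to 35 days.
- C3c: the enrolment approach will "allow women to enroll at any time/stage of the menstrual cycle".
- C1: an earlier study in 37 women found "craving to smoking cues elevated in the follicular phases, relative to the luteal phases" (p = .02). A later study in 93 women found that the ratio itself correlated with craving (p < .05), while the separate hormone measures did not reach significance.
- C3j, Aim 2 Hypothesis 3: the ratio enters a linear model directly, and linearity is checked.
- C3i: power is calculated for gender and treatment contrasts. At least 80% power is asserted for the remaining hypotheses, with no effect size or calculation for this one.

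**The concern.** One hypothesis needs one estimate and one test. Here there are two analyses with no order between them, and the second ends in two or three separate sets of slopes. The text does not say what result would support the hypothesis, what happens if one segment is positive and another negative, or how the several tests are controlled. The predictor in the segment step is hormone measures in general, not the ratio. No repeated-measures model is named, although a woman can contribute up to 14 × 4 × 2 = 112 post-cue ratings (C3e: 14 days, four sessions a day, two cues a session). Within-woman and between-woman association are not separated.

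The reason given for segmenting does not lead to it. A curved path of the ratio over time says nothing about the shape of craving as a function of the ratio. The measured daily ratio can be a time-varying covariate whatever its path, and Aim 2 Hypothesis 3 already treats it directly.

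At stake is whether the study can give a clear answer on ovarian hormones, which C3b gives as the reason for oversampling women.

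**Working it through.** **1. The plan's own power figure.** C3i states that "a sample of 96 females and 48 males is necessary to achieve 90% power", "with a two sided type I error rate of 0.05", for d = 0.50 with a correlation of 0.70. For one measure per person, power = Φ(0.50 × √(96 × 48/144) − 1.96) = Φ(2.83 − 1.96) = 80.7%. With m equally correlated measures the variance factor is (1 + (m − 1) × 0.70)/m. At m = 5 it is 0.76, and power = Φ(2.83/√0.76 − 1.96) = 90.0%. The document does not state m. The figure therefore reproduces, but it concerns the gender contrast and gives no benchmark for Hypothesis 2.

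**2. Complexity of the segment fit, per hormone profile, from about 14 daily values.**
- Simplest form, two continuous linear segments: 3 coefficients + 1 knot = 4 parameters.
- Most complex form, three quadratic segments: 3 × 3 + 2 knots = 11 parameters unconstrained, or 7 + 2 = 9 if continuous.
- Choice of shapes: 2² + 2³ = 12.

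Because women start at any cycle stage, the first segment of one woman need not match the first segment of another.

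**3. Number of tests.** Suppose any significant segment counted as success, each tested at 0.05 unadjusted and independently:
- two segments: 1 − 0.95² = 9.75%
- three segments: 1 − 0.95³ = 14.3%
- three segments plus two phase tests: 1 − 0.95⁵ = 22.6%, an upper case.

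If only slopes in the hypothesised direction counted (0.025 each), two and three segments give 4.9% and 7.3%, against 2.5% for one test.

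**4. Information lost within segments.** Let f be the share of within-woman variance of the ratio that lies between segments. Take as benchmark a single slope over all 14 days with 80% power (noncentrality 1.96 + 0.84 = 2.80). Both f and the benchmark are assumptions.
- Pooled within-segment slope: Φ(2.80 × √(1 − f) − 1.96).
- One of k equally informative segments: Φ(2.80 × √((1 − f)/k) − 1.96).

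| f | pooled | one of two | one of three |
|---|---|---|---|
| 0 | 80% | 51% | 37% |
| 0.25 | 68% | 40% | 29% |
| 0.50 | 51% | 29% | 21% |
| 0.75 | 29% | 17% | 12% |

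**5. Is that range of f plausible?** An illustrative simulation assumed a 28-day log-ratio profile with a high first half, a fall of 2 units over four days, a low plateau and a late rise. It took a 14-day window from a random start, fitted continuous linear segments with best-fitting knots to the ratio, and used daily noise SDs of 0.2, 0.4 and 0.8. It gave f of 0.44, 0.36 and 0.23 with two segments, and 0.76, 0.63 and 0.43 with three. The profile and noise are assumed, so this shows only that the loss can be material without being complete.

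**The case against.** The strongest reply is that the segments come on top of the phase analysis. A reader might infer that the plan removes the follicular/luteal contrast, where the team's earlier data showed a difference. C3j does not support that, because it keeps the phase grouping and describes the segments as an extension. What remains is narrower: the text does not say whether the grouped analysis compares phases or fits within them, or which analysis decides.

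Other points on that side also stand:
- A reader might infer that the knot search itself inflates type I error. It does not, because knots are fitted to hormones and not to craving. Any inflation comes from several unadjusted tests, and the plan never says that one significant segment would be enough. The 23% case needs five independent tests, but phase and segment tests reuse the same data.
- The 9 to 11 parameters apply only to the most complex permitted form. The text also does not say that each woman is fitted without pooling.
- The power loss assumes that only within-woman variation is used. Pooling women by segment number would keep some cross-phase variation, mixed with differences between women.
- The earlier phase study does not report the ratio and leaves the hormonal cause open, so it does not prove that the ratio signal lies between segments. The direct ratio evidence in 93 women came from one cue session and is between-woman.

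None of this supplies a deciding test.

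**Conclusion.** The point holds in this form: Hypothesis 2 has two analyses with neither primary. The segment analysis yields two or three sets of slopes with no combined test of the ratio, no rule for disagreement and no stated repeated-measures model. It also leaves between-segment ratio differences unused. The argument from non-linearity over time does not justify it and sits badly with Aim 2 Hypothesis 3.

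The absence of a deciding test is plain from C3j and rests on no assumption. The sizes are illustrations. Pooled power of 68%, 51% or 29% depends on assumed shares of 25%, 50% or 75% and on an assumed 80% benchmark. The 9.75% to 14.3% error depends on independent tests and on counting any segment as success. The documents support neither a fixed power loss nor a fixed error rate, because they give no effect size and no success rule for this hypothesis. This should be corrected before the analysis. It does not affect the design or the data collected.

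**What to change.** Name one primary model in women: a mixed model of post-cue craving on that day's log(estradiol/progesterone), split into the woman's own mean and her daily deviation, each interacted with cue type. Adjust for pre-cue craving, presentation order and study day, and include random subject effects.

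Name one deciding test, because separate smoking and stressful cue terms would again leave two coefficients. Either:
- the coefficient of daily deviation × active versus neutral cue, matching the stimulus factor in Hypothesis 1; or
- a joint or Holm-adjusted test of the smoking and stressful cue coefficients.

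Report the between-woman (mean) coefficient alongside, since the Specific Aims do not say which association is meant. Check curvature with a spline in the log ratio. Keep the phase and segment analyses, labelled exploratory.

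The cost is wording in C3j, on the same data. The downside is that the primary test assumes one log-linear slope, which the spline checks.

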**THE GENDER-SEX HORMONE INTERFACE WITH CRAVING & STRESS-RELATED CHANGES IN
SMOKING**

NCT#01576874

Protocol Version 12, IRB-approved January 12, 2016

THE GENDER-SEX HORMONE INTERFACE WITH CRAVING & STRESS-RELATED CHANGES IN SMOKING

SPECIFIC AIMS

Despite considerable advances in treatment development, cigarette smoking remains the leading cause of preventable death in the United States, and most smokers engaged in treatment are unsuccessful in quitting. The burden of illness is disproportionately borne by female smokers, who are less responsive to cessation interventions than males. The relationships between stress, craving, and smoking behavior are recognized as key factors underlying gender differences in nicotine dependence, but must be better understood and characterized to yield avenues for interventions addressing this critical health disparity.

In prior and ongoing SCOR studies, our research team has demonstrated gender and menstrual cycle/sex hormone influences on reactivity to laboratory-presented cues. Building from these laboratory findings, we propose taking two important next steps: (1) evaluating the experience of craving in the “real world” natural environment of female and male smokers, and (2) examining the impact of a safe and novel pharmacological intervention (oxytocin) on stress reactivity in female and male smokers.

During a 2-week period, participants will use the newly developed and validated Cue Reactivity Ecological Momentary Assessment (CREMA) software implemented on a widely available personal digital assistant (iPhone) to provide real-time responses to stressful, smoking-related, and neutral picture cues presented multiple times daily in their natural environment. Additionally, daily saliva samples will be used to determine sex hormone (estradiol, progesterone, and testosterone) levels. These procedures will provide an unprecedented opportunity to prospectively and continuously evaluate dynamic sex hormone influences on cue-responsive craving in the “real world” natural environment of smokers.

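### Aim 1 Hypothesis 2 names no by-woman effect and does not separate within-woman from between-woman hormone variation, so its slope can blend the two

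*Combined protocol and SAP*

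**What the plan says.** Section C3j, Aim 1 Hypothesis 2, describes two analyses of the 14 days of saliva and CREMA data in women. One is the conventional follicular/luteal grouping. The other fits a piecewise linear or quadratic curve, with estimated knots, to the individual's hormone profile. After that, "regression models assessing hormone measures against the outcome (e.g., cue-elicited craving) in each segment will be assessed". For this hormone–craving step the section mentions no random or fixed subject effect, no centring on the woman's mean, and no change term.

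The neighbouring analyses are more explicit. Aim 1 Hypothesis 1 has a linear mixed model. Aim 2 Hypotheses 1 and 2 have a random subject effect. Aim 2 Hypothesis 3 enters both the prior week's change in the ratio and the same-day ratio.

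The Specific Aims say that daily sampling gives the chance to "prospectively and continuously evaluate dynamic sex hormone influences on cue-responsive craving". Section C1 says of earlier work that "it remained unclear whether progesterone effects may be static versus dynamic", and explains the two words as where the hormone stands at one moment against how it moves.

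Baseline variables are screened as possible covariates by comparing gender and treatment groups (C3j, Statistical Analysis), not by their relation to hormone level.

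**The concern.** A woman-day can have a high ratio for two reasons: she usually runs high, or that day is high for her. The first is a comparison between different women and is open to confounding by anything stable that goes with both hormone level and cue reactivity, such as age or smoking intensity. The second is the comparison that daily sampling was designed to give. A single slope on pooled woman-days averages the two. Cluster-robust errors correct the standard error but leave the estimate a blend, and a random intercept only reduces the between-women share.

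The phase comparison has the same feature. Women may enter at any cycle stage and give 14 days of a 25–35 day cycle, that is 14/35 = 40% to 14/25 = 56%. Follicular and luteal days therefore come partly from different women.

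At stake is whether a difference between kinds of women could be reported as a day-to-day hormone effect on craving.

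**Working it through.** **The plan's own figure.** The only full calculation (C3i) is for the gender comparison in Aim 1 Hypothesis 1: "a sample of 96 females and 48 males is necessary to achieve 90% power", "with a two sided type I error rate of 0.05", with a difference of 0.45 on an SD of 0.9 (d = 0.50). Repeated ratings are allowed for "through a between-observation correlation (autocorrelation) of 0.70". Take 0.70 as exchangeable over m ratings (m is not stated) and multiply the variance by f = (1 + (m − 1) × 0.70)/m. Power with 96 and 48 is then 80.7% at m = 1, 89.5% at m = 4 (f = 0.775) and 91.5% at m = 14 (f = 0.721). The stated 90% reproduces, as does 144/(1 − 0.20) = 180 recruits. None of this addresses a hormone slope, and no hormone effect size is given.

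**Inputs for the check.** From the documents: 96 women, 14 days, SD 0.9, correlation 0.70. Read as exchangeable, these give a between-woman craving variance of 0.70 × 0.81 = 0.567 (SD 0.753) and a within-woman variance of 0.243 (SD 0.493). Assumed, because the documents give no figure: between-woman share of hormone variance k = 0.2, 0.4 or 0.6; correlation r between a woman's stable hormone level and her stable craving = 0 to 0.4; day-to-day hormone AR(1) of 0.7; independent daily craving errors. The true within-woman effect is zero.

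**Expected false slope when pooled.** Per SD of hormone, slope = r × 0.753 × √k. For r = 0.3 and k = 0.4 this is 0.3 × 0.753 × 0.632 = 0.143; the simulated mean was 0.140. Over r = 0.2 to 0.4 and all k, simulated slopes ran from 0.07 to 0.23 craving units.

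**Rejection rates at two-sided 5%.** 2,000 runs per setting; Monte Carlo standard error near 5% is √(0.05 × 0.95/2000) = 0.5 points. Ranges are over k.

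| Days | r | Pooled, cluster-robust | Random intercept, uncentred | Within-woman |
|---|---|---|---|---|
| 14 | 0 | 5.2–6.8% | 4.4–5.4% | 4.2–6.1% |
| 14 | 0.2 | 25–41% | 5.0–8.5% | 4.9–5.7% |
| 14 | 0.3 | 48–77% | 6.9–11.9% | 5.1–5.9% |
| 14 | 0.4 | 72–95% | 6.8–14.6% | 4.5–5.7% |
| 5 | 0 | 5.7–6.4% | 5.0–5.5% | 5.0–5.7% |
| 5 | 0.2 | 17–36% | 6.3–14.1% | 4.0–5.1% |
| 5 | 0.3 | 34–69% | 8.7–26.1% | 4.5–5.5% |
| 5 | 0.4 | 51–90% | 11.8–40.2% | 4.4–5.3% |

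Five days stands for one segment, since two or three segments in 14 days leave about 5 to 7 days each. The random intercept does worse there because it removes a fraction 1 − 0.493/√(0.243 + T × 0.567) of each woman's mean: 0.83 at T = 14 but 0.72 at T = 5.

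Ignoring clustering altogether, the pooled 14-day test rejects in 37–48% of runs even at r = 0. That is a standard-error fault, separate from confounding.

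**A different set-up.** With an assumed cycle shift of 1.0 in the log ratio, between-woman SD 0.3–0.7, day noise 0.3 and r = 0.2–0.3, pooled cluster-robust rejection was 33–81%. The uncentred random intercept gave 6–14% (8–28% on follicular days only) and the within-woman term about 5%. A further run gave 29–76%, 6–12% (7–26%) and 4–6%; at r = 0 all three were about 4–7%.

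**Precision after separation.** The slope detectable with 80% power is 2.80 × 0.493/√(96 × 13) = 0.04 per within-woman SD. For the between-women term it is 2.80 × √(0.567 + 0.243/14)/√95 = 0.22 per between-woman SD.

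**The case against.** The strongest reply is that this is silence, not a stated error. The text speaks of hormone measures, and section C1 uses similar words for level and percentage change alike. The curve is fitted to the individual's profile; if the segment regressions were also run woman by woman, they would already be within-woman. That stands: a reader might infer that the plan enters the raw level, but it does not say so. Nor does it say that the regressions are per woman, or how about 5 to 7 days per segment would be combined across women.

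A reader might also infer that the plan puts 70% of craving variance between women. It does not. The 0.70 is a correlation between observations, also called an autocorrelation, in the gender power calculation. Read instead as a pure day-to-day AR(1), it would leave a woman's 14-day mean with about 33% of the variance. The simulated sizes and the precision figures rest on the exchangeable reading.

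The 30–80% is for a pooled model that the plan never names. With the mixed-model family used in adjacent hypotheses, the all-days inflation is modest. That too stands.

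If the outcome is active-minus-neutral craving, stable craving level cancels and only stable reactivity can confound. Entry at any cycle stage dilutes the confounding. Neither separates the two effects.

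Finally, within versus between is not the same distinction as section C1's level versus change. A deviation from the woman's mean is still a same-day level, re-centred. That is correct and shapes the fix.

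**Conclusion.** The concern holds as a gap in specification. Aim 1 Hypothesis 2 states neither how repeated days from one woman are handled nor whether its target is the within-woman or the between-women association, and the confounder screen does not cover hormone level. Carried out as written on pooled woman-days, the slope blends the two.

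Under the stated assumptions and a trait correlation of 0.2–0.3, false-positive rates are roughly 30–80% for pooled cluster-robust regression, about 6–14% for an uncentred random intercept over 14 days and higher within one phase or segment, and about 5% for a within-woman term. At zero trait correlation, cluster-robust pooling is close to nominal. The trait correlation and the hormone variance split are not in the documents, so these are illustrations and not the error rate of the planned test.

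The documents do not support the stronger conclusion that the study cannot address dynamic hormone influence. The data can; the analysis is not yet specified so that it does. The gender power calculation is unaffected.

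**What to change.** In Aim 1 Hypothesis 2, fit a mixed model for cue-elicited craving (active cue with the neutral cue as control) with a by-woman random intercept and slope. Enter two terms: the woman's mean log estradiol/progesterone ratio, and each day's deviation from that mean. Name the daily-deviation coefficient as the test of the within-woman, day-to-day question. Report the between-women coefficient separately, noting that a woman's mean depends on which part of her cycle was sampled.

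Keep the phase and segmented analyses, using the same two terms in each. If section C1's question about movement in level is to be tested, add a day-to-day change term, because the deviation does not answer it.

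The cost is wording in the plan and two derived variables (three with the change term), with no new data or visits. The downside is that the pooled slope is no longer the headline result. The hypothesis, now worded only as a positive relation among women, would also have to say which relation it means.
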